### Amber criteria (where no amber criteria exist, the green criteria apply):

- At least 6/8 schools are successfully recruited, randomised and retained throughout the study
- Participation rates at intervention and control schools retained in the trial are at least:
  - 60% of teacher-reported SDQ at baseline. 80% retained at follow-up.
  - 60% of child-report Stirling Wellbeing Questionnaire at baseline. 60% retained at follow-up.
- Any differences in the characteristics of the children with missing data on teacher report measures (when compared to those with complete data) are able to be handled successfully via statistical methods.
- There is evidence of at least adequate reliability for scan observations, focal observations and assessment of physical activity.

### 3.5 Secondary endpoints/outcomes

N/A

## 3.6 Exploratory endpoints/outcomes

N/A

### 3.7 Table of endpoints/outcomes

Objectives	Outcome Measures	Timepoint(s) of evaluation of this outcome measure (if applicable)
Primary Objective To determine the feasibility of progressing to a cluster RCT (with intervention and waitlist arms) of an outdoor play programme for primary/junior schools which aims to improve the quality of children's outdoor play as a route to decreasing children's risk for mental health problems and improving children's wellbeing and enjoyment of school.	Outcomes are the progression criteria (see above)	Monitored throughout the study

Secondary Objectives Example: To assess the safety of treatment A in <insert condition="" population=""></insert>	N/A	
Tertiary Objectives Please add if applicable, otherwise delete this row	N/A	

#### 4 TRIAL DESIGN

The study is a feasibility RCT using a cross-over design (but note that outcomes are not assessed post-intervention in the waitlist group due to time constraints) with usual practice as the control condition. The full RCT would be designed to test the superiority of the intervention when compared to usual practice.

#### 5 TRIAL SETTING

The trial will be run through eight participating schools. Participating schools will be referred to the trial through OPAL once they have approached them and agreed to do the programme.

#### 6 PARTICIPANT ELIGIBILITY CRITERIA

#### 6.1 Inclusion criteria

Schools must be at least single form entry (~30 children per year or more). Schools will initially be recruited through pre-specified regions covering the SW of England (Cornwall, Devon, Bristol, Bath, Dorset and Wiltshire). If necessary this area may be expanded.

#### 6.2 Exclusion criteria

Schools who primarily support children with Special Educational Needs or Developmental Disorders will not be included because the intervention is designed for mainstream schools at this stage.

Although recruitment focuses on the school level, note that data will not be collected about children in years 5 and 6 because they will have left the schools by the post-intervention phase.

### 7 TRIAL PROCEDURES

From January 2024 to July 2024 schools who contact OPAL and agree to complete the programme will be assessed for eligibility to participate in the study until eight schools have been recruited.

Eligible schools will be given information by OPAL about the research and asked to consent to OPAL providing the research team with their contact details. If they consent, the relevant OPAL mentor for the region will provide the research team with these contact details.

The research team will then contact the school to discuss participation, providing detailed information sheets, which will have been assessed and approved by the University of Exeter ethics committee.

The research team will answer any questions the school may have and then ask the head teacher to provide consent for the school to participate in the research.

If consent is given, baseline data collection will be scheduled. The baseline data collection period takes an estimated 7 weeks. This will be scheduled for the next available slot.

Once baseline data collection is complete, schools will be randomised to either the intervention or control condition. Randomisation will be done in pairs of schools to allow the intervention to begin as soon as possible, rather than waiting for baseline measures to be complete at all 8 schools.

Focal observations of play will be conducted at all schools allocated to the intervention arm. When these are complete, the research team will inform the OPAL mentor that they can begin the programme.

After 18 months, data collection will be completed at all intervention and control schools who remain in the trial.

Control schools will then complete the intervention.

Interviews will be conducted at baseline, 9 months and 12 months as a process evaluation.

Qualitative interviews will be conducted at the end of the intervention (at intervention schools) to evaluate experiences and outcomes of the intervention.

#### 7.1 Recruitment

From January 2024 to July 2024 schools who contact OPAL and agree to complete the programme will be assessed for eligibility to participate in the study until 8 schools have been recruited.

Eligible schools will be given information by OPAL about the research and asked to consent to OPAL providing the research team with their contact details. If they consent, the relevant OPAL mentor for the region will provide the research team with these contact details.

The research team will then contact the school to discuss participation, providing detailed information sheets, which will have been assessed and approved by the University of Exeter ethics committee.

The research team will answer any questions the school may have and then ask the head teacher to provide consent for the school to participate in the research.

The OPAL mentors will be asked to keep a record of the number of schools who were ineligible as well as those who were eligible but declined to be contacted about the research; characteristics of these schools and reasons will be recorded where possible.

The research team will keep records of the number of schools who consented to be contacted but did not consent to participate in the research. Characteristics of these schools and reasons will be recorded where possible.

### 7.1.1 Participant identification

The three OPAL mentors covering the South-West regions will identify participants (schools). The research team will provide them with our eligibility criteria and information sheets about the research. When a new school signs an agreement with them to complete the OPAL intervention, the mentor will assess the school for eligibility as a research participant. If they are eligible, they will give them the information sheets and seek consent for the research team to contact the school about participation.

### 7.1.2 Screening

None

### 7.1.3 Payment

We will pay for all eight schools to receive the OPAL programme. We will pay OPAL directly. Alongside the intervention, schools will receive financial support of £2500 to cover the cost of staff time to support the research. £1250 will be paid to each school after completion of baseline data, and £1250 will be paid to each school after completion of follow up data.

In addition, parents and schools staff will receive £5 vouchers in return for their time completing questionnaires. School staff who take part in process evaluation interview or the qualitative research will be given a £20 voucher in return for their time.

### 7.2 Consent

Headteachers will be given detailed study information sheets and will provide informed consent for the school to participate in the research. The OPAL intervention falls within usual curriculum and other institutional activities (BPS, code of human ethics 2010, p.17) so no additional consent from parents is required for the intervention to be ran at the school. The headteacher will provide informed consent for all children in their care in Years 3 and 4 at baseline to complete questionnaires and for teachers of children in Year R to Year 4 to complete a questionnaire for all children in their class. They will also give consent for playtimes to be observed, but only in a way that does not lead to individual-level data (e.g. how many children are climbing?).

Parents will have a right to refuse their child's participation and children will have the right to refuse to participate. In both cases, no reason needs to be given and there will be no adverse consequences.

Children will be told about the research generally in a school assembly led by the research team, once before the baseline data collection, and again before the post-test data collection. During this assembly we will give children the opportunity to ask questions and explain what they should do if they don't want to take part or if they have any questions later on. In both cases they should speak to their teacher who can let us know. Prior to completing the measures in class, children will be shown a short animation explaining what they are being asked to do and why. This will explain that they can choose not to answer the questions if they don't want to and that they can ask their teacher if they have any questions. Researchers will then answer any questions the children may have before they hand out the questionnaires.

Parents will be given information about the trial which will include contact details. The process for withdrawing data and consent will be explained in this information sheet.

Parents will give active consent for completing questionnaires about their child, for their child to be observed playing (in a way that leads to information about an individual child's play) and for their child to participate in a qualitative interview. Parent will be able to consent to any, all, or none of these, as they wish; there will be no pressure to consent.

School staff will give active consent for completing questionnaires about playtime and for participating in qualitative interviews.

# 7.2.1 Additional consent provisions for collection and use of participant data and biological specimens in ancillary studies, if applicable

n/a

#### 7.3 The randomisation scheme

Method of randomisation is simple randomisation with a 1:1 allocation ratio. Schools will be randomised one pair at a time.

### 7.3.1 Method of implementing the randomisation/allocation sequence

Schools will be randomised to the intervention (OPAL) or usual school practice arm in a 1:1 ratio using blocked randomisation of 4 blocks of two. An independent statistician will conduct randomisation via a computer-generated algorithm. Schools will be randomised after school enrolment and baseline assessments have been completed. The independent statistician will pass the allocation to the research team who will inform schools and parents/carers which arm they are allocated to.

### 7.4 Blinding

It is not possible for participants to be blind or to guarantee that observers will be blind because the changes made to playtime will likely be obvious. To minimise bias, the post-test observers will not be explicitly told which condition each school is in whilst conducting the main evaluation (they will be unblinded for the focal observations as these are only conducted at the intervention schools). Study statisticians will remain blind to school/participant trial arm at least until completion of the primary analyses. Health economists will need to be unblinded in order to conduct economic analyses.

### 7.5 Emergency Unblinding

N/A

### 7.6 Baseline data

Baseline data includes:

- Parent-report questionnaires
- Teacher-report questionnaires
- Child-report questionnaires
- Observations of play

Other measures and information are sought via interviews for a qualitative evaluation of the intervention and process evaluation of the intervention implementation and research.

Each are outlined in the table below under relevant headings. Note that most measures are included because they would be used in a full RCT to examine the primary or secondary outcomes, or to examine whether the programme successfully changes play (the proposed mechanism through which the programme would affect mental health). We have explained the relevance of each measure to a full RCT. Because this is a feasibility trial, the research questions focus on the feasibility of using these measures within a full RCT.

Parent report measures		
ars R-4 (at baseline)		
The data will be used to describe the sample and to ensure sufficient diversity in the focal observation subsample (see below), where we want to ensure diversity in child sex, age, ethnicity and wellbeing.		
Child internalising problems, as measured via the SDQ internalising subscale would be compared from baseline to posttest.		
We will use the Ofsted questionnaire to give us insight into whether the play programme has affected children's enjoyment of school and parent's perceptions of the school in a broad sense.		
The CHU9D will be used in a full RCT for health economics evaluation by providing Quality Adjusted Life Years (QALYS).		
The resource use questionnaire will be used in a full RCT for health economics evaluation, comparing service use between those who attend the intervention school and those who attend control schools.		

(children YR to Y4 at baseline)		
SDQ with impact section	Child internalising problems, as measured via the SDQ internalising subscale would be compared from baseline to posttest (likely primary outcome measure for full RCT).	
Child self-report measures		
Activities During Playtime questionnaire	This measure allows children to tell us about what they play and will provide insight into how play has changed in terms of activities. It contributes to analysis of the extent to which the programme changes play (the proposed action through which is may affect mental health).	
Emotions during playtime	The measure will be completed on two occasions at baseline and two occasions at post- intervention. Scores for negative affect and positive affect will be averaged together to give one baseline score per child and one post-test score per child. Scores on specific items related to adventurous play (excited, scared, fearless, daring) will also be averaged across the two completions to allow examination of changes in these emotions over time. Finally, the item 'lonely' will be averaged across the two completions and examined as a potential factor that may change as a result of the intervention.	
How I feel about my school questionnaire	Items will be summed to give an overall score for positive feelings about school. This will be used to evaluate change from baseline to post-intervention.	
Autonomy in Play and Challenge in Play Scales	Items will be summed to give an overall score for each scale. This will be used to contribute to an evaluation of change in play from baseline to post-intervention.	
Social interaction during breaktime (1 question)	In a larger scale RCT we may include changes in social interaction within statistical models to control for the influence that this may have no wellbeing.	
Stirling Children's Wellbeing scale	It is planned that the wellbeing scale will serve as a secondary outcome in a full RCT.	
School staff report		
(all school staff involved in the planning and supervision of playtimes)		
Supervisor Risk Engagement and Protection Survey [S-REPS]	One of the targets of the programme will be supervisors' attitudes to risk. In particular, supervisors will be encouraged to consider	

	allowing children to assess their risk more independently, and to
	consider the risk-benefit profile of a behaviour rather than to simply seeking to reduce all risk. We will thus compare self-reported attitudes before and after the programme.
Supervisor report of breaktime activity (bespoke questionnaire)	Responses will contribute to the assessment of whether play has changed as a result of the intervention.
Supervisor report of barriers to implementing play interventions.	We are interested to see whether the OPAL programme is able to address all of these barriers and whether addressing them is linked to changes in children's play.
Observations of play	
Multidimensional Toolkit for the Assessment of Play in Schools (M-TAPS) Scan observations.	During the M-TAPS scan observations, the entire playground is scanned and observers count each: 1) activity type; 2) probability of adventure; 3) affect; 4) physical activity level.  Activity count data will feed into evaluation of changes in play between pre and post-intervention.
Intervention schools only:  Multidimensional Toolkit for the Assessment of Play in Schools (M-TAPS) Focal observations.	A subsample of 40 children from each intervention school (160 total) from Years 1-4 (at baseline) will be observed in focal observations. 20 of these children will have at least 'slightly elevated' (a score of 4 or higher) scores on the SDQ emotional difficulties scale based on parent measures at baseline; 20 will be age and gender matched controls whose scores on the SDQ emotional problems subscale are within the 'Close to average' range.
	Focal playground observations capture activity type, probability of adventure, affect and activity level of each child in the focal subsample.
	All children will be observed twice and then averaged together across days. Reliability assessments will be conducted on approximately 20% of the observations. Intra-class correlation will be used to evaluate reliability of coding.
	The data collected will be used to contribute to the evaluation of how play has changes from baseline to post-intervention (including an evaluation of whether changes are seen for both groups of selected children).
	groupe of colocica crimarony.

Additional measures and information				
Qualitative interviews with children about their experiences of the playtimes (post-intervention only).	Qualitative interviews will be conducted to determine the pros and cons of the play programme from children's perspectives. These will be crucial for determining whether the programme had any unexpected effects on children that were not captured by other measures. It will also provide a more in-depth understanding of the programme from the child's perspective.			
Qualitative interviews with school staff about their experiences of the OPAL intervention (post-intervention only.	Qualitative interviews will be conducted to determine the pros and cons of the adventurous play programme. These will be crucial for determining whether the programme had any unexpected adverse or positive effects on children and school staff that were not captured by other measures. These will also be used to identify any perceived barriers to implementing the programme that can be resolved prior to a full trial.			
Process evaluation interviews	The OPAL mentor delivering the programme, headteacher and the school lead(s) for implementation at the intervention schools will be interviewed at baseline, 9- and 18-months. Headteachers from the control schools (and any other staff who have been involved heavily in the research) will be interviewed at 18 months only.			
	Qualitative interviews will be conducted to capture how they believe the programme will 'work' in that school, any issues that arise during implementation and whether and how the changes will be sustained.			

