#### Green criteria:

- No serious concerns have arisen about the acceptability of study procedures
- At least 7/8 schools are successfully recruited, randomised and retained throughout the study
- Participation rates at intervention and control schools retained in the trial are at least:
  - 80% of teacher-reported SDQ at baseline. 80% retained at follow-up.
  - 80% of child-report Stirling Wellbeing Questionnaire at baseline. 80% retained at follow-up.
- No marked differences in the characteristics of the children with missing data on teacher report measures when compared to those with complete data.
- Evidence that play has improved at intervention schools, based on at least two of the following: scan observations, focal observations, child-report and school-staff report,
- There is evidence of at least good reliability for scan observations, focal observations and assessment of physical activity.
- Measures used capture range of costs and benefits based on process evaluation and qualitative interviews.

- No serious negative impacts have arisen.

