## 2.2 Data quality and standards

**Questionnaire data:** online standardised questionnaires will be used where available. Where paper copies are used, they will be entered into Qualtrics and at least 10% will be checked by a second team member for accuracy. Surveys will be set-up to highlight any missed questions to participants. Data will be exported to CSV files.

**Observation data:** Coders will be trained to be reliable (at least ICC = .8/Kappa = .8) by the PI prior to data collection. Coders live coding will be checked periodically to ensure reliability is maintained.

**Qualitative data:** Interviews will be conducted using a topic guide with detailed field notes kept.

Detailed records of the data collection processes will be made to support data sharing.

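### Coder agreement is the only reliability method fixed for the focal observations, and it cannot show how reliable the score used is, which is each child's mean over two days

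*Protocol*

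**What the plan says.** The Trial Summary lists, among the objectives, finding out whether reliable data on play and physical activity can be collected. Reliability is also a progression criterion. The Green list in Section 3.4 reads "There is evidence of at least good reliability for scan observations, focal observations and assessment of physical activity", and the Amber list lowers this to adequate. Neither names a type of reliability or a cut-off.

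Two places say how reliability is assessed:

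- Section 7.6, focal observations: "Reliability assessments will be conducted on approximately 20% of the observations", followed by "Intra-class correlation will be used to evaluate reliability of coding".
- Section 11, data management plan item 2.2: "Coders will be trained to be reliable (at least ICC = .8/Kappa = .8) by the PI prior to data collection", with periodic checks of live coding afterwards.

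Both concern coders. Section 10 lists a reliability analysis for scans, focal observations and physical activity without saying which kind.

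On the score itself, Section 7.6 says: "All children will be observed twice and then averaged together across days". The focal subsample is 40 children at each intervention school, 160 in all. Half have raised parent-reported SDQ emotional scores and half are matched children with scores close to average. The data feed the judgement of how play changed, overall and in each of the two groups.

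**The concern.** The one reliability statistic that the protocol commits to does not describe the score that the protocol uses. Two coders who watch the same child at the same playtime both see whatever that day produced: the weather, the playmates, the child's mood. Their agreement says nothing about whether another day would look similar. For a mean of two days, that is the larger question about reliability whenever day-to-day variation exceeds coder error.

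The two daily observations on every focal child would answer it, but the protocol plans only to average them. A feasibility trial is where one should learn whether two days are enough. As written, the trial could report good reliability for focal observation, take the measure into a definitive trial with two days per child, and never have examined that choice.

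**Working it through.** **Inputs from the protocol.** Eight schools are randomised 1:1 in four blocks of two (Section 7.3.1), so four are intervention schools. 4 × 40 = 160 children, which reproduces the stated total. Two observations each give 320 per wave; 20% of these is 64. The coder training threshold is 0.8. No between-day variance or ICC is given anywhere.

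**Model.** Split the variance of a single observation into a stable child share *s*, a child-by-day share *d* and a coder-error share *e*, with *s* + *d* + *e* = 1. Assume day and coder errors are independent across the two days. Then:

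- coder ICC = *s* + *d*
- single-day between-day ICC = *s*
- reliability of the two-day mean = *s* / (*s* + (*d* + *e*)/2) = 2*s*/(1 + *s*), which is Spearman-Brown for two days.

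The day share *d* adds to the first quantity and lowers the third.

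**Two-day reliability with the coder ICC held at 0.80 (values of *s* assumed).**

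| *s* | 2*s*/(1 + *s*) |
|---|---|
| 0.80 (no day variation) | 0.89 |
| 0.60 | 0.75 |
| 0.40 | 0.57 |
| 0.30 | 0.46 |
| 0.20 | 0.33 |
| 0.08 | 0.15 |

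For *s* = 0.5 the formula gives 1.0/1.5 = 0.67. Reliability falls below 0.50 when *s* is below 1/3. At a coder ICC of 0.80, that means less than 0.333/0.80 = 42% of the coder-agreed variance is stable between days.

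**The two figures can move in opposite directions.** Fix child variance at 1 and coder variance at 1, and let day variance be 0, 1, 3 and 6. The coder ICC, (1 + day)/(2 + day), rises: 0.50, 0.67, 0.80, 0.88. The two-day reliability, 1/(1 + (day + 1)/2), falls: 0.67, 0.50, 0.33, 0.22.

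**Simulation of the planned check.** 160 children, two days, 64 double-coded observations, 2,000 runs, assumed true coder ICC 0.85. With *s* = 0.30 the observed coder ICC was at least 0.80 in 90% of runs, while the mean estimated two-day reliability was 0.45. With *s* = 0.20 the figures were 89% and 0.33.

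**What it does to an analysis.** The SD of the two-day score is 1/√reliability times the SD of the stable child component. For *s* = 0.2, 0.3 and 0.5 that is 1.73, 1.47 and 1.22. A change standardised by the observed SD shrinks by the inverse: 0.58, 0.68 and 0.82. The raw mean change is unaffected.

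**Can the trial estimate it?** The approximate standard error of a between-day ICC of 0.3 from 160 children is (1 − 0.3²)/√159 = 0.91/12.61 = 0.07. The 95% range is about 0.16 to 0.44, or 0.27 to 0.61 for the two-day mean. This ignores clustering by school and the matched selection, so it is optimistic, but the estimate is precise enough to be useful.

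**The case against.** The strongest reply is that the protocol contradicts nothing. Saying that an ICC assesses coding is not saying that coding is all that will be assessed. The criterion and Section 10 speak of reliability without a type, and an analysis plan not seen here could add a between-day ICC. That stands as a limit. Still, the only method the protocol fixes is tied to coders, and nothing in it requires a between-day figure before reliability is called good.

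Some stronger readings are tempting, and the documents do not support them:

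- **A reader might infer that the focal score is mostly noise.** No between-day variance is given, and the assumed values above run from 0.15 to 0.89.
- **A reader might infer that noise dilutes the measured change or the contrast between the SDQ groups.** Section 10 plans differences in unadjusted means without significance tests, and the groups are set by baseline parent SDQ, not by the focal score. Independent day noise biases neither raw difference.
- **A reader might infer that the coder check is met by construction.** The 0.8 is a threshold for training before collection. Live coding can drift between waves about 18 months apart, and no number is attached to good or adequate.
- **A reader might infer that an ICC is wrong for activity type.** Activity type may be scored as counts, for which an ICC is suitable, and the data management plan names kappa as well.

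The weight of the measure is also limited. Focal observation takes place only at intervention schools and is one of four sources for improved play, any two of which suffice.

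**Conclusion.** The point holds in a limited form. The reliability method fixed in Sections 7.6 and 11 describes the coding, whereas the quantity analysed is a two-day mean whose stability that method cannot show. A favourable coder ICC is compatible with two-day reliability of 0.33, 0.46 or 0.67 under assumed between-day ICCs of 0.2, 0.3 or 0.5. The true value is unknown, so this is a possible misjudgement of the criterion, not a demonstrated one.

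The consequence is lost precision, a larger SD and weaker standardised or child-level use. That SD would be the right one for another two-day design, but planners could not tell how much of it further days would remove. At *s* = 0.3, for instance, four days would give (4 × 0.3)/(1 + 3 × 0.3) = 1.2/1.9 = 0.63 in place of 0.46. Day effects shared by a whole school, such as weather, lie outside this model and would not average out over children. The change is worth making because it is cheap; the measure itself has not been shown to be unsound.

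**What to change.** In Sections 7.6 and 10, keep the coder ICC. Add, at baseline and separately at post-intervention, the between-day ICC from the two observations of each focal child. Account for school and SDQ selection group, since a pooled figure would count differences between schools and between the selected groups as child stability. Give a confidence interval and the Spearman-Brown reliability of the two-day mean.

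In Section 3.4, state that the coder ICC alone supports only a conclusion about coding reliability, and that the two-day figure will be considered beside it when the reliability criterion is judged and when the number of observation days for a full trial is chosen. The 0.8 training threshold should not be carried over as a cut-off for the two-day mean. It was set for coders, and a score can serve group-level change with less.

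The cost is one extra analysis of data already planned and a few sentences of text. The downside is that the reported reliability may look less favourable.
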